### Group 5 (EGFRmut, T790M-, MET GCN $\geq$ 5, 2L, EGFR TKI resistant)

An interim analysis for futility will be performed based on stage 1 of the 2-stage design of Group 5 when 10 participants have completed at least 2 tumor assessments while on treatment with capmatinib monotherapy, had radiological disease progression per RECIST 1.1, or discontinued capmatinib monotherapy treatment prior that time. Recruitment will be on temporary halt while conducting the IA. The IA will be based on the EAS.

The decision to stop for futility at the interim analysis will be based on the predictive probability (PP) that the final observed ORR of capmatinib monotherapy is no worse than the historical control ORR, given the interim observed data (x) and responders among n participants. Based on available data (Soria et al 2015, Mok et al 2017), the ORR in the historical control for this population is expected to be around 35%. Thus, the stop for futility rule is based on

$$PP = \text{Prob}[\text{Final observed ORR of capmatinib monotherapy} \geq 35\% \mid x, n]$$

A minimally informative Beta distribution prior with prior mean equal to 35% will be used, i.e., the prior distribution will be Beta (0.5385, 1) for the futility stopping decision rule calculations at the interim analysis.

The group will be stopped for futility at the interim analysis if the PP <1%, i.e., if 0 response out of the first evaluable 10 participants is observed. For the purpose of the interim analysis a responder is defined as participant having a response of PR or CR per RECIST 1.1.

All evaluable participants at the time of the data cut-off for the interim analysis will be used to obtain the futility boundary using the stopping criteria. The futility boundary will be calculated according to the actual number of evaluable participants (in the EAS) in the interim analysis.

Table 10-3 presents the PP at the final analysis based on different numbers of responders observed at the interim analysis and an observed ORR of not worse than 0.35 for capmatinib monotherapy.

**Table 10-3 Predictive probability (PP) for ORR of capmatinib monotherapy at the final analysis based on various numbers of responders observed at the IA for Group 5**

Responders at IA out of 10 evaluable participants at IA	Predictive probability (PP)
0	0.0000
1	0.0148
2	0.0984
3	0.3207
4	0.6301
5	0.8686
6	0.9720
7	0.9967
8	0.9998
9	1.0000
10	1.0000

With 10 evaluable participants for the interim analysis, if no (0) response is observed (PP <1%), the Group 5 will be stopped for futility.

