### 10.6.2 Statistical model, hypothesis, and method of analysis

The analysis of the primary endpoint will be performed for participants in the EAS who were treated with capmatinib monotherapy and based on the time period of monotherapy treatment. ORR is defined as the proportion of participants with confirmed best overall response of CR or PR, and will be assessed by the investigator according to RECIST 1.1.

The analysis of Group 5 data will be performed when all participants enrolled in the group have completed at least 6 treatment cycles (about 6 months) or discontinued prior to that time for any reason, provided the Group 5 continued into Stage 2.

The primary efficacy endpoint ORR will be estimated and the 2-sided exact 95% CI (Clopper and Pearson 1934) provided. Capmatinib monotherapy treatment will be considered to have clinically relevant efficacy if the following criteria are fulfilled:

- the ORR estimate is > 45% and
- the lower bound of the two-sided 95% exact CI is >35%.

Based on historical data (Soria et al 2015, Mok et al 2017), the ORR in this population is expected to be around 35% and the threshold of 45% is considered of clinical interest.

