### Group 3 (EGFRmut, T790M negative, any MET, 1L antineoplastic)

One interim analysis for futility will be performed for participants enrolled in Group 3 (participants in first line setting) when approximately 20 participants have completed at least 4 cycles of treatment or discontinued treatment prior that time. A close monitoring of the first 20 measurable participants will be performed. All evaluable participants at the time of the data cut-off for the interim analysis will be used.

The decision whether to continue or stop enrollment and/or treatment will be based on the probability of success (PoS). PoS is the probability to have a positive conclusion at the end of the study, given the interim data. Denoting the number of participants at interim by  $n_1$  and the number of responders at interim by  $r_1$ , PoS is found as

- $PoS = \text{Prob} [\text{at least } x-r_1 \text{ responders in } 40-n_1 \text{ participants} \mid r_1 \text{ responders in } n_1 \text{ participants}]$

The number of responders ( $x-r_1$ ) to be observed in the remaining  $40-n_1$  participants follows a Beta-binomial distribution. This is used in order to calculate PoS.

The enrollment and/or treatment may be stopped at the interim analysis if  $PoS < 0.10$ , i.e., if less than 9 out of the first 20 participants have the best response of CR or PR. The criterion (number of responders) will be based on the actual number of participants in the FAS at the time of the interim analysis.

If futility is concluded, the enrollment of 1L participants (Group 3 and 1L participants in Group 4) may be stopped. The enrollment in opened groups with pre-treated participants will continue.

[Table 10-2](#) provides the probabilities of success at the primary analysis based on different numbers of responders observed at the interim analysis. For 9 or more responders PoS exceeds 0.10 and the study will continue at interim.

**Table 10-2 Probability of success at the primary analysis based on various numbers of responders observed at the IA for Group 3**

Responders at IA out of 20 evaluable participants at IA	Probability of Success
8/20	0.04
9/20	0.14
10/20	0.33
11/20	0.57
12/20	0.79

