**Group 5 (EGFRmut, T790M-, MET GCN  $\geq$  5, 2L, EGFR TKI resistant)**

The operating characteristics (with 30 participants and assuming an interim analysis after Stage 1 at 10 participants) were determined for the primary objective to estimate the treatment effect of capmatinib monotherapy. Based on available data ([Soria et al 2015](#), [Moket al 2017](#)), the ORR in the historical control for this population is expected to be around 35%. The success criterion defined in [Section 10.5.2](#) requires an estimated ORR of  $>45\%$  and a lower bound of the two-sided 95% exact CI of  $>35\%$  to conclude that the antitumor activity is of clinical interest.

[Table 10-7](#) presents the probability of stopping at the interim analysis, the probability for a positive conclusion (i.e., not stopped at IA for futility and success criteria met at final analysis after stage 2) and for a negative conclusion (i.e., not stopped at IA for futility but success criteria not met at final analysis) under different underlying true ORR of capmatinib monotherapy.

The operating characteristics have up to around 35% probability of stopping the trial for futility when the true ORR is  $\leq 35\%$ . Also, when the true ORR is 45% then the probability of positive conclusion at the final analysis with 30 participants is ca. 50%. If the true ORR is 50% or higher, the probability of a positive conclusion at the final analysis with 30 participants is  $>70\%$ .

To adjust for potential discordance between local vs central MET amplification testing results, additional participants may be enrolled to ensure there are at least 10 in stage 1 and 30 in total MET amplified participants centrally confirmed by Novartis-designated laboratory.

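### The Group 5 futility rule predicts a final ORR of at least 35% rather than the trial's own success criterion, so it stops only at 0/10 and continues at 1/10, where success is very unlikely on either reading of that criterion

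*Protocol*

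**What the plan says.** **Interim rule (Section 10.9, Group 5).** The decision is "based on the predictive probability (PP) that the final observed ORR of capmatinib monotherapy is no worse than the historical control ORR", given as 35%. On the prior: "the prior distribution will be Beta (0.5385, 1) for the futility stopping decision rule calculations at the interim analysis". On the threshold: "The group will be stopped for futility at the interim analysis if the PP <1"%, which the protocol equates with 0 responses in 10.

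**Success (Section 10.6.2).** Two conditions must both hold: "the ORR estimate is > 45% and" "the lower bound of the two-sided 95% exact CI is >35"%. Section 10.10 repeats them.

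**What the interim is said to estimate.** Section 8.5 (Phase II part) says the Group 5 interim analysis will estimate the probability of success of the trial and refers to the interim analysis section for details. The only definition of that term there is under Group 3: "PoS is the probability to have a positive conclusion at the end of the study, given the interim data".

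**Operating characteristics (Section 10.10, Group 5).** They are calculated "with 30 participants and assuming an interim analysis after Stage 1 at 10 participants". The text says they "have up to around 35% probability of stopping the trial for futility when the true ORR is" at most 35%. Table 10-7 gives 34.87% at a true ORR of 10%, 10.74% at 20% and 1.35% at 35%.

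**The concern.** A futility rule is meant to stop a group that can no longer reach a positive conclusion. This one predicts an event that is not a positive conclusion: a final 11/30 passes the interim target and fails both success conditions. Group 3's rule predicts success. Group 5's does not, and no reason is given, although Section 8.5 describes both interims in the same terms.

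At stake are up to 20 further participants treated in stage 2 when success is already out of reach, and a reader's belief that the interim guards against a rate no better than the historical one. The summary sentence in Section 10.10 encourages that belief, because its figure of about 35% belongs to a true ORR of 10%.

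**Working it through.** **Inputs.** Prior Beta(0.5385, 1), interim n = 10, final n = 30, threshold 1% (Sections 10.9 and 10.10); success conditions (Section 10.6.2).

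**Step 1: convert each target to a count out of 30.**
- Interim target, ORR of at least 35%: 0.35 × 30 = 10.5, so at least 11.
- ORR above 45%: 0.45 × 30 = 13.5, so at least 14.
- Clopper-Pearson lower bound above 35%: 34.3% at 16/30 and 37.4% at 17/30, so at least 17. This is the binding condition.

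**Step 2: predictive probability.** With x responders in 10, the number Y among the remaining 20 follows BetaBinomial(20, 0.5385 + x, 11 − x), and PP = P(Y ≥ r − x) for a final target of r.

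| x of 10 | Table 10-3 | r = 11 | r = 14 (ORR above 45% alone) | r = 17 (both conditions) |
|---|---|---|---|---|
| 0 | 0.0000 | 0.0006 | 0.00004 | 0.000001 |
| 1 | 0.0148 | 0.0148 | 0.0017 | 0.0001 |
| 2 | 0.0984 | 0.0984 | 0.0197 | 0.0021 |
| 3 | 0.3207 | 0.3207 | 0.1046 | 0.0201 |
| 4 | 0.6301 | 0.6301 | 0.3157 | 0.1012 |

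With r = 11, Table 10-3 is reproduced. The only difference is 0.0006 against a printed 0.0000 at x = 0, which changes no decision. Applying the same 1% threshold to success moves the boundary to 2/10 or fewer when r = 17, and to 1/10 or fewer when r = 14.

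Under the written criterion, success after 1/10 needs 16 of the next 20, and after 2/10 it needs 15 of 20. If the true ORR were 50%, those conditional chances would be 0.6% and 2.1%.

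**Step 3: probability of stopping**, P(X ≤ c) with X ~ Binomial(10, p).

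| True ORR | 0/10 (current) | 1/10 or fewer | 2/10 or fewer |
|---|---|---|---|
| 10% | 34.87% | 73.61% | 92.98% |
| 20% | 10.74% | 37.58% | 67.78% |
| 30% | 2.82% | 14.93% | 38.28% |
| 35% | 1.35% | 8.60% | 26.16% |
| 45% | 0.25% | 2.33% | 9.96% |
| 50% | 0.10% | 1.07% | 5.47% |
| 55% | 0.03% | 0.45% | 2.74% |

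The first column agrees with Table 10-7.

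**Step 4: which success count Table 10-7 uses.** Summing P(X = x) × P(Y ≥ r − x) over x above the boundary, with Y ~ Binomial(20, p) and stopping at 0/10:

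| True ORR | Table 10-7, positive conclusion | r = 14 | r = 17 |
|---|---|---|---|
| 35% | 12.63% | 12.63% | 1.24% |
| 45% | 49.75% | 49.75% | 13.56% |
| 50% | 70.76% | 70.76% | 29.23% |

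Every positive-conclusion entry in the table reproduces with r = 14, not with r = 17. The protocol's text and its table therefore use different success rules.

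**Step 5: cost in success probability.**
- Written criterion, moving from 0/10 to 2/10 or fewer: 29.23% to 29.14% at ORR 50%, 50.25% to 50.11% at 55%, 71.45% to 71.31% at 60%. The largest loss is 0.14 points.
- ORR above 45% alone, moving from 0/10 to 1/10 or fewer: 49.75% to 49.63% at ORR 45%, 70.76% to 70.63% at 50%. The largest loss is 0.13 points.

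**The case against.** The rule is disclosed. Section 10.9 gives the target, prior, threshold and boundary; Table 10-3 follows from them; Table 10-7 prints the 1.35%. Section 10.6.1 frames Group 5 as estimating the contribution of monotherapy, and a rule that stops only for apparent inactivity can suit that aim. The Group 5 stop is also worded as mandatory and the Group 3 stop as optional, which is a reason for more leniency in Group 5. All of this stands as a possible rationale, but the protocol does not offer it, and Section 8.5 says the interim estimates something else.

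Stopping early has costs. Section 10.2.3 ties the combination efficacy analysis to completion of both stages, so a stop forfeits it. At a true ORR of 45%, the level Section 10.6.2 calls of clinical interest, stopping at 2/10 or fewer would end the group 10.0% of the time. Both points stand and belong in any revision.

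A reader might infer four stronger things that the documents do not support:
- That the interim gives no protection. It stops 34.87% of the time at ORR 10% and 10.74% at 20%, which is weak but not nothing.
- That 2/10 or fewer is the one correct boundary. This depends on the written criterion. Under 14/30, PP at 2/10 is 1.97%, above the threshold, and using that boundary would cost 1.1 to 1.2 points (49.75% to 48.63% at ORR 45%; 70.76% to 69.53% at 50%).
- That continuing at 3/10 is also wrong. PP there is 2.0% under the written criterion, so a success-based rule at 1% continues as well.
- That the sentence quoting about 35% is false. It is literally the maximum over the tabulated rates; it is misleading, not wrong.

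The interim counts any PR or CR whereas the final ORR needs confirmation. This is minor, because some responses cannot yet be confirmed at the interim.

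**Conclusion.** The concern holds as a mismatch between the futility target and the success criterion, and as a conflict between Section 8.5 and Section 10.9. It is not an arithmetic error in Table 10-3. A boundary of 0/10 is too lenient for a rule aimed at success on either reading: at 1/10 the predictive probability of success is 0.01% (17/30) or 0.17% (14/30), both well below the protocol's own 1%. At 2/10 the answer turns on the reading, 0.21% or 1.97%.

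At a true ORR of 35%, the group would continue from 1/10 or 2/10 in 26.16% − 1.35% = 24.8% of trials. These figures assume the protocol's prior and exactly 10 and 30 evaluable participants.

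**What to change.** 1. Reconcile the written success criterion (17/30) with Table 10-7 (14/30). The boundary depends on this.
2. In Section 10.9, define PP for Group 5 as the predictive probability of meeting the Section 10.6.2 success criterion. Keep the 1% threshold and the existing recalculation for the actual interim n. At n = 10 this gives stop at 2/10 or fewer under the written joint criterion, or 1/10 or fewer if success is ORR above 45% alone.
3. Recompute Tables 10-3 and 10-7 and align Section 8.5 with the rule used.
4. In Section 10.10, replace the figure of about 35% with the stopping probability at ORR 35%: 1.35% under the current rule, 26.2% or 8.6% under the revised boundaries.
5. State the downsides. Stopping at 2/10 or fewer costs at most about 0.15 points of success probability under the written criterion, with stops 10.0%, 5.5% and 2.7% of the time at true ORR 45%, 50% and 55%. Stopping at 1/10 or fewer also costs at most about 0.15 points, with 2.3% stops at ORR 45%. Either forfeits the combination analysis when it stops.

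The change itself is protocol wording and two recomputed tables. If the sponsor prefers the 35% target, for example to protect the combination analysis, the protocol should give that reason and stop describing the quantity in Section 8.5 as the probability of success.

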Participants with clinical evidence of bone metastases must have a whole body bone scan at baseline per local institutional practice (e.g., Tc99m bone scan, NaF positron emission tomography (PET) or whole body bone MRI). Lesions identified on the whole body bone scan at baseline, which are not visible on the chest and abdomen CT (or MRI) scan should be imaged

at baseline and followed at subsequent scheduled visits using localized CT, MRI or X-ray. After baseline, whole body bone scans need not be repeated, unless clinically indicated.

Skin lesions present at baseline should be documented using color photography, including a ruler, so that the size of the lesion(s) can be determined from the photograph. Skin photographs should be continued at subsequent tumor assessments for any lesions that were photographed at screening.

Baseline brain CT or MRI will be mandated for all participants prior to study treatment. Subsequent brain scans should only be conducted if brain lesions are documented at baseline for eligible participants or in participants that develop symptoms indicative of brain metastases.

All CRs and PRs must be confirmed by a second assessment not earlier than 4 weeks after the criteria for response are first met.

Any potentially measurable lesion that has been previously treated with radiotherapy should be considered as a non-measurable lesion. However, if a lesion previously treated with radiotherapy has clearly progressed since the radiotherapy, it can be considered as a measurable lesion.

PET/CT may be used only if the CT is of similar diagnostic quality as a CT performed without PET, including the utilization of oral and intravenous contrast media.

All participants discontinuing from the study for PD must have their disease progression documented by radiologic evaluation. In cases of clinically-evident disease progression, all efforts should be made to perform a radiologic evaluation.

Participants with symptoms of rapidly progressing disease without radiological evidence will be classified as progression only when clear evidence of clinical deterioration is documented and/or participant discontinued due to ‘Disease progression’ or death due to study indication.

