### Phase II part of the study

This is a single arm trial (i.e. no comparator arm) and there is no a priori information as per the FDA Guidance of "situations in which safety concerns may be unusually high" or the participant population being studied are "potentially fragile population such as children, pregnant women or the very elderly, or other vulnerable populations, such as those who are terminally ill or of diminished mental capacity." Thus, an independent data monitoring committee will not be constituted for the Phase II part of this study.

The Novartis clinical team will review the safety data on a regular basis. A review of the safety data and assessment of futility, based on the calculated Bayesian probability of success (PoS) will be performed at the interim analysis of Group 3 (first line) by the Novartis clinical trial team and shared with the investigators in a data review meeting.

At the time of the interim analysis for Group 3, the best overall response for each participant will be derived from the overall lesion response assessments performed by the Investigator. These will be used to calculate the overall response rate for the respective group and a Bayesian analysis will be performed to estimate the PoS of the trial given the current data (see [Section 10.9](#) for details).

It is envisioned that the team may make three types of recommendations at the interim analysis, namely:

- No safety or efficacy issues, ethical to continue the study group as planned
- PoS is too small and the study group is terminated due to lack of significant activity
- Serious safety concerns precluding further treatment in the study group, regardless of efficacy.

At the time of the interim analysis for Group 5, the response for each participant will be derived from the overall lesion response assessments performed by the Investigator. These will be used to calculate the ORR and a Bayesian analysis will be performed to estimate the POS of the trial given the current data (see [Section 10.9](#) for details).

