- Discontinuation of study treatment for any reason (other than starting combination treatment or new anti-cancer therapy): BOR will take into account all response assessments irrespective of the reasons for discontinuing capmatinib monotherapy (treatment policy strategy)
- Any unforeseen intercurrent events (e.g., related to a public health emergency) will be handled by the treatment policy strategy

5. Summary measure: ORR defined as the proportion of participants with confirmed BOR of CR or PR based on investigator assessment per RECIST 1.1

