**Table 10-7 Operating characteristics for various assumed true ORR of capmatinib monotherapy**

True ORR	Probability to stop at IA* (%)	Probability of positive conclusion at final analysis (%)	Probability of negative conclusion at final analysis
0.10	34.87	0.00	65.13
0.20	10.74	0.09	89.17
0.25	5.63	0.82	93.55
0.30	2.82	4.00	93.17
0.35	1.35	12.63	86.02

True ORR	Probability to stop at IA* (%)	Probability of positive conclusion at final analysis (%)	Probability of negative conclusion at final analysis
0.40	0.60	28.55	70.85
0.45	0.25	49.75	50.00
0.50	0.10	70.76	29.14
0.55	0.03	86.44	13.53

\*Assuming interim analysis at 10 evaluable participants

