- PR = at least two determinations of PR or better at least 4 weeks apart before progression (and not qualifying for a CR) where confirmation required or one determination of PR prior to progression where confirmation not required
- SD = at least one SD assessment (or better) > 6 weeks after randomization/start of treatment (and not qualifying for CR or PR).
- PD = progression  $\leq$  12 weeks after randomization/ start of treatment (and not qualifying for CR, PR or SD).

- UNK = all other cases (i.e. not qualifying for confirmed CR or PR and without SD after more than 6 weeks or early progression within the first 12 weeks)

The time durations specified in the SD/PD/UNK definitions above are defaults based on a 6 week tumor assessment frequency. However these may be modified for specific indications which are more or less aggressive. In addition, it is envisaged that the time duration may also take into account assessment windows. E.g. if the assessment occurs every 6 weeks with a time window of +/- 7 days, a BOR of SD would require a SD or better response longer than 5 weeks after randomization/start of treatment.

Overall lesion responses of CR must stay the same until progression sets in, with the exception of a UNK status. A patient who had a CR cannot subsequently have a lower status other than a PD, e.g. PR or SD, as this would imply a progression based on one or more lesions reappearing, in which case the status would become a PD.

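### The Group 5 futility look counts any PR or CR, so a response that can no longer be confirmed can keep the group open although the predictive probability is for the final, confirmed ORR

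*Protocol*

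**What the plan says.** **Interim count.** Section 10.9 (Group 5) gives the look its own definition: "For the purpose of the interim analysis a responder is defined as participant having a response of PR or CR per RECIST 1.1". Section 8.5 agrees: "At the time of the interim analysis for Group 5, the response for each participant will be derived from the overall lesion response" assessments made by the investigator. The neighbouring text for Group 3 in Section 8.5 uses best overall response instead.

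**Final endpoint.** Section 10.6.1 has "ORR defined as the proportion of participants with confirmed BOR of CR or PR based on investigator assessment per RECIST 1.1", and Section 10.6.2 repeats it: "ORR is defined as the proportion of participants with confirmed best overall response of CR or PR". Section 7.2.1 adds: "All CRs and PRs must be confirmed by a second assessment not earlier than 4 weeks after the criteria for response are first met". Section 14.1.3.1 makes the order explicit: "PR = at least two determinations of PR or better at least 4 weeks apart before progression". Under the estimand, responses after a switch to the combination or after new anticancer therapy are non-responses.

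**Timing.** The look takes place when "10 participants have completed at least 2 tumor assessments while on treatment with capmatinib monotherapy, had radiological disease progression per RECIST 1.1", or discontinued earlier. Scans are every 8 weeks from the start of Cycle 3 (Section 7.2.1).

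**Rule.** The group stops if PP, the predictive probability that the final observed ORR is at least 35%, is below 1%. With 10 evaluable participants this means 0 responses. Table 10-7 gives "Probability to stop at IA" by true ORR.

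**The concern.** PP adds the interim responder count to a predicted number of future responders and asks whether the total reaches the final target. That is coherent only if a participant counted at the interim can also count at the end. The interim definition drops confirmation, and the look is late enough for some responses to have failed visibly by then. PR at about week 8 with PD at about week 16 is such a case: PR needs two determinations before progression, so this participant cannot be a responder at the final analysis.

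With 10 evaluable participants, a single count separates stopping from continuing. One response already known to have failed can therefore open stage 2, and 20 more participants are enrolled with no interim response that can count at the end. The same mismatch sits behind Table 10-7, where one rate stands for both the interim and the final response.

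**Working it through.** **Inputs from the protocol.** Prior Beta(0.5385, 1); 10 participants at the interim and 30 at the end (20 remaining); target ORR of at least 35%. Since 0.35 × 30 = 10.5, at least 11 of 30 are needed. Stop if PP < 1%.

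**Step 1: reproduce Table 10-3.** With x interim responders the posterior is Beta(0.5385 + x, 11 − x), and PP is the beta-binomial probability of at least 11 − x responders among the remaining 20.

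| x | PP recomputed | Table 10-3 |
|---|---|---|
| 0 | 0.0006 | 0.0000 |
| 1 | 0.0148 | 0.0148 |
| 2 | 0.0984 | 0.0984 |
| 3 | 0.3207 | 0.3207 |

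The rows for x = 4 to 10 also agree to four decimals. At x = 0 the printed value differs slightly, but both values are below 1%. In this calculation all x interim responders are carried forward as final responders.

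**Step 2: one failed PR.** Suppose none of the 10 participants has a confirmed or confirmable response, and one had PR at the first scan and PD at the second.

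- Counted as the final endpoint will count it: x = 0, PP = 0.0006, stop.
- Counted under Section 10.9: x = 1, PP = 0.0148, continue.

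The boundary depends on the number evaluable. With 11 evaluable and 30 in total, x = 1 gives 0.0077 (stop) and x = 2 gives 0.0608 (continue), so the same problem arises one count higher.

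**Step 3: reproduce the stopping column of Table 10-7.** P(0 of 10) = (1 − p)^10, with p the true ORR. For p = 0.10 this is 0.90^10 = 34.87%; for p = 0.20 it is 0.80^10 = 10.74%. Every row reproduces. The same p also drives the positive-conclusion column, which concerns the final ORR, so the table models neither failed confirmation nor a first response after the interim.

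**Step 4: sensitivity.** Let f be the share of first PR/CRs that fail confirmation and l the share of eventual confirmed responders with no PR or CR yet at the interim. The interim response rate is q = p(1 − l)/(1 − f), and the stopping probability is (1 − q)^10. The protocol gives neither f nor l; the values below are assumptions.

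| Confirmed ORR p | Table 10-7 | f = 10%, l = 0 | f = 20%, l = 0 | f = 10%, l = 20% |
|---|---|---|---|---|
| 0.10 | 34.87% | 30.8% | 26.3% | 39.4% |
| 0.20 | 10.74% | 8.1% | 5.6% | 14.1% |

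Worked entries at p = 0.10:

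- f = 20%, l = 0: q = 0.10/0.80 = 0.125 and 0.875^10 = 26.3%.
- f = 10%, l = 20%: q = 0.10 × 0.80/0.90 = 0.0889 and 0.9111^10 = 39.4%.

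If l = f, then q = p and the table's figure is exact.

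**The case against.** **The wording may already imply confirmation.** The definition refers to RECIST 1.1, Section 7.2.1 requires all CRs and PRs to be confirmed, and Section 14.1.3.1 requires confirmation in non-randomized trials with response as the primary endpoint. This reading is possible but less literal: the sentence is a special definition for the interim, and it omits the word that Sections 10.6.1 and 10.6.2 both include. If confirmation was meant, the sentence still needs correcting.

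**Leniency may be deliberate.** A generous count is a common choice at a futility-only look, and it does not loosen the final success criteria. That stands for responses still awaiting confirmation. It does not justify counting responses already known to have failed.

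**Table 10-7.** A reader might infer that the stated stopping probabilities are simply too high. The documents do not support that. Failed confirmation lowers the true stopping probability, but late first responses raise it. Scans continue after the interim, and the estimand keeps responses after discontinuation of monotherapy unless the combination or a new therapy has started. Section 10.6.1 cites a median time to response of about 6 weeks, which suggests that late responses may be modest in number, but a median does not bound the tail.

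**Size.** Where the true ORR is near the historical 35%, the rule hardly ever stops: 1.35% as stated, and 0.7% or 0.3% with f = 10% or 20% and no late responses. This objection stands; the issue matters mainly at low ORR.

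**Conclusion.** The mismatch is real and follows from the text alone: the interim count admits responses that the final endpoint will reject, while PP treats them as final responses. With 10 evaluable participants, one PR already lost to progression changes the decision (PP 0.0006 to 0.0148). This needs no assumed rate, only the literal reading of the interim definition.

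The effect on Table 10-7 is conditional. If failed confirmation of 10% to 20% were the only departure, stopping would be 30.8% to 26.3% instead of 34.87% at ORR 0.10, and 8.1% to 5.6% instead of 10.74% at ORR 0.20. Late responses can cancel or reverse this, so neither the size nor the direction of the net error is established. What can be said is that the table rests on an unstated assumption: every interim response is confirmed and none arises later.

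**What to change.** In Section 10.9 (Group 5), define the interim responder as a participant with a confirmed CR/PR, or with a CR/PR still pending confirmation. State that a CR/PR followed by PD, a switch to the combination or new anticancer therapy before confirmation is a non-response. A PR followed by SD would stay pending, because the worked example in Section 14.1.3.1 allows a later PR to confirm it. Point the Group 5 sentence in Section 8.5 to the same definition.

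Add a note to Table 10-7 that its figures assume all interim responses are confirmed and none arise later.

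The cost is a sentence and a table note, with no extra data. The small downside is that the group stops slightly more often than under the present wording. The change does not make the interim count identical to the final endpoint, since some pending responses will fail, and it does not guarantee the Table 10-7 figures. It removes only the cases already known to be wrong.
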